6.3.2 Best Overall Response

The best overall response is the best response recorded from the start of the treatment until disease progression/recurrence (taking as reference for progressive disease the smallest measurements recorded since the treatment started). The patient's best response assignment will depend on the achievement of both measurement and confirmation criteria.

6.3.3 Duration of Response

The duration of response (DOR) is measured from the time measurement criteria are met for CR or PR (whichever is recorded first) until the first date that recurrent or progressive disease is objectively documented (taking as reference for progressive disease the smallest measurements recorded since the treatment started), death, or, in the absence of PD, date of last assessment.

6.3.4 Event-Free Survival

Event-free survival (EFS) is defined as the duration of time from the date of study enrollment until time of disease relapse, disease progression, alternative anti-lymphoma therapy, or death, whichever occurs first.

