1.10.2 Number and duration of cycles

As noted above, allogeneic stem cell transplantation is the only curative treatment for R/R TCMs. The proposed regimen was therefore primarily developed as 1) an induction regimen for patient who are not in at least a partial remission, and are therefore not eligible for a transplant, and 2) a bridge to an allogeneic hematopoietic stem cell transplant (alloSCT) for patients who have residual disease after one or more systemic treatment and therefore have refractory lymphoma, although they may be considered a transplant candidate. Patients with lymphoid malignancies who respond to most treatment, including the drugs used in this regimen, do so within the first 4 cycles of treatment. Total number of cycles is therefore limited to 6 in this trial.

With our clinical experience in aggressive TCM at NIH particularly with ATLL showing progression within 4 weeks, treatment cycle is set as every 3 weeks (every 21 days). A shorter treatment cycle will also allow for more frequent response evaluations and more timely referrals for an alloSCT. If the proposed treatment schedule is consistently associated with prolonged neutropenia requiring treatment delays in the majority of patients, the protocol will be amended to administer treatment every 4 weeks (every 28 days).

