3 STUDY IMPLEMENTATION

3.1 STUDY DESIGN

To determine the maximum tolerated dose (MTD), and the safety and toxicity profile of the combination of lenalidomide, CC-486 (5-azacitidine) and romidepsin in patients with refractory/relapsed TCM, a phase 1 open-label, non-randomized, single-center study will be conducted at the NCI. A standard “3 + 3” design will be used to determine the MTD of dose-escalated lenalidomide in combination with fixed doses of CC-486 (5-azacitidine), romidepsin (R) and dexamethasone (D) with an expansion cohort at the MTD.

In patients with relapsed or refractory TCM, lenalidomide will be administered by oral intake in a dose-escalation with a starting dose of 5mg daily, a second dose level of 10mg daily, a third dose level at 15mg daily, and a fourth dose level at 20mg daily on days -7 to day 10 of first cycle (see **Table 1** for additional dose levels and schedules, cycles are 21 days each). After the second cycle, lenalidomide will be given from day 1 to day 10 in each cycle for up to six cycles. CC-486 (5-azacitidine) with a dose of 300mg oral intake daily will be given on day 1 to day 10, romidepsin will be administered at a dose of 12 mg/ m² on days 1 and 10 (±2 days) and dexamethasone will be given on day 1 and 10 (±2 days) of the cycle.

After approval of Amendment 12/07/2022: Participants will receive six cycles (each 28 days in length) of: lenalidomide at the MTD from day 1 to day 10, CC-486 (5-azacitidine) at a dose of 300mg oral intake daily given on day 1 to day 10, romidepsin administered at a dose of 12 mg/ m² on days 1 and 10 (±2 days) and dexamethasone on day 1 and 10 (±2 days) of the cycle.

Treatment will continue for a maximum of 6 cycles or until toxicity (i.e., dose limiting toxicity) as found in Section 3.9 or toxicity requiring discontinuation as defined in Section 3.5) or progressive disease.

The treatment will be repeated for up to 6 cycles. The patients are allowed to proceed to stem cell transplantation (SCT) if eligible during and after the protocol treatment. Patients who undergo SCT before all 6 cycles of protocol treatment are administered will be taken off therapy. All patients who undergo SCT will continue to be followed for survival, but not for toxicity (see Section 3.8)

Cycles 1-6												28
Azacitidine												by mouth once per day
Lenalidomide												by mouth once per day
D												D
R												R

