¹ 30 days (± 7) following last dose of any study drug (via clinic or phone). If initiating new anti-cancer therapy within 30 days after last dose of any study drug, 30-day safety follow-up visit must occur before first dose of new therapy.

² Screening and Baseline evaluations should be performed within 28 days prior to enrollment and dosing, respectively, unless otherwise noted and with the following exceptions: Confirmation of diagnosis (no time limit); HIV antibody, HTLV-1/2 serologies, Hepatitis B surface antigen and Hepatitis C antibody, EKG, TTE, bone marrow aspiration/biopsy and Clonal T-cell receptor rearrangement by PCR (all within 3 months), baseline pregnancy testing (within 10 – 14 days and within 24 hours prior to prescribing lenalidomide) **NOTE:** Any screening tests performed within the specified time frame for baseline do not need to be repeated.

³ To be performed on Day 21 (± 2 days) of Cycles 2, 4, and 6. Confirmatory scans should also be obtained 4 weeks following initial documentation of objective response.

⁴ To be done at end of treatment (30 days after last dose of study treatment; may be combined with 30 day safety follow-up, if timing coincides). If subject to initiate new anti-cancer therapy assessments should occur before the first dose of the new therapy.

⁵ Follow-up to occur about every 60 days (± 7 days) for first 6 months, every 90 days (± 14 days) for 2 years, then every 6 months (± 28 days) for another 2 years and then annually (± 6 weeks) until disease progression or initiation of new anti-cancer therapy.

⁶ After disease progression or initiation of new anti-cancer therapy, contact for survival about every 3 to 6 months (± 4 weeks).

⁷ Pathologic review/confirmation of diagnosis by Laboratory of Pathology, NCI (no time limit). If archival sample is not available or not adequate, a fresh tumor biopsy and/or peripheral blood sample will be obtained.

⁸ Complete medical history at screening/baseline. Interim on study and in follow-up. Disease and social history required only at screening.

⁹ Physical exams to include vitals, weight, and height (screening only).

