6.3.5 Progression-Free Survival

Progression-free survival (PFS) is defined as the duration of time from the date of study enrollment until time of disease relapse, disease progression, or death, whichever occurs first.

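### The regimen is meant to lead to allogeneic transplant, but no endpoint or analysis rule says how a transplant enters EFS, PFS, DOR or response rate

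*Combined protocol and SAP*

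**What the plan says.** **Purpose.** Section 1.10.2 calls allogeneic SCT the only curative option and describes the regimen as induction for patients not yet eligible and as "a bridge to an allogeneic hematopoietic stem cell transplant (alloSCT) for patients who have residual disease". Section 3.1 adds: "The patients are allowed to proceed to stem cell transplantation (SCT) if eligible during and after the protocol treatment". It also says: "Patients who undergo SCT before all 6 cycles of protocol treatment are administered will be taken off therapy". After SCT it promises follow-up for survival but not for toxicity, and does not name disease status.

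**Time-to-event endpoints.**
- EFS (6.3.4) runs from enrollment "until time of disease relapse, disease progression, alternative anti-lymphoma therapy, or death, whichever occurs first".
- PFS (6.3.5) runs from enrollment "until time of disease relapse, disease progression, or death, whichever occurs first".
- Section 10.4.3 censors EFS, PFS and OS at last follow-up, and DOR also at last follow-up.
- Section 6.3.3 ends DOR at progression or death or, without progression, at the last assessment.
- Section 6.3.1.2 (CTCL) uses the off-treatment date for DOR and TTP when a patient stops treatment for any reason.

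**Disease follow-up.** Section 3.8.2 collects disease status only until new anti-neoplastic therapy, progression, death or study end. Section 3.8.3 moves anyone starting new anti-cancer therapy to survival contact.

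**Response.** Section 6.3.2 says that "best response assignment will depend on the achievement of both measurement and confirmation criteria". Footnote 3 of the study calendar (3.9) reads: "Confirmatory scans should also be obtained 4 weeks following initial documentation of objective response". Footnote 4 places end-of-treatment assessments before the first dose of any new anti-cancer therapy. The RECIL table in 6.3.1.1 has no confirmation criterion; the CTCL criteria do.

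**The concern.** Remission followed by transplant is the outcome that the regimen is built to produce, yet two analysts following this plan could code the same patient in opposite ways.

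In EFS, the patient may be an event on the day of transplant or may remain event-free. In PFS, the time after transplant counts as progression-free up to last follow-up. If SCT is new anti-neoplastic therapy, no disease assessment is scheduled in that time. In DOR, the answer depends on which of three sections is followed. In ORR, the patient may be an unconfirmed responder.

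The trial is uncontrolled, so no comparison cancels the coding choice. If the choice is left until the data are seen, it can be made between materially different results.

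**Working it through.** **1. Figures in the plan.** The plan states no figure for these endpoints: no expected SCT rate, power, effect size or event count. Its only design figures concern DLT, and they reproduce. The probability of escalating is (1−p)³ + 3p(1−p)²(1−p)³; at p = 0.5 this is 0.125 + 0.047 = 0.172, against the stated 0.17. They do not bear on this point.

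**2. Where SCT falls under each rule.**

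| Endpoint | Rule | Effect of SCT in remission |
|---|---|---|
| EFS, 6.3.4 | Alternative anti-lymphoma therapy is an event; term undefined | Event or not, depending on the analyst |
| PFS, 6.3.5 and 10.4.3 | No SCT rule; censored at last follow-up | Post-SCT time counts; post-SCT deaths are events |
| DOR, 10.4.3 | Censored at last follow-up | Post-SCT time counts |
| DOR, 6.3.3 | Ends at last assessment | May stop before SCT |
| DOR, 6.3.1.2 (CTCL) | Off-treatment date | Does not run past SCT given on treatment |

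The CTCL rule matters for the escalation cohort, which included CTCL patients (1.10.3). The expansion cohort excludes them.

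**3. Size for EFS and PFS (illustration).**

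Inputs:
- Median PFS without SCT: 4 months. Section 1.6.1 gives this for romidepsin alone; applying it here is an assumption.
- Exponential times; a share q of 20-50% of those progression-free at month 3 is transplanted, independently of prognosis (assumed).
- Post-SCT hazard h times the earlier one, with h = 0.25, 0.5 or 1 (assumed).

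Formulas, with λ = ln 2 / 4 = 0.1733 per month:
- Without SCT: S(3) = e^(−3λ) = 0.595 and S(12) = e^(−12λ) = 0.125.
- SCT as event: (1−q) × S(12). For q = 0.2 this is 0.100; for q = 0.5 it is 0.0625.
- Censored at SCT: 0.125, given the independence assumed above.
- Carried through: (1−q) × S(12) + q × S(3) × e^(−9hλ). For q = 0.5 and h = 0.25: 0.0625 + 0.5 × 0.595 × 0.677 = 0.264. For h = 1 it is 0.125 at any q.

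| Handling of SCT | 12-month estimate | Median (months) |
|---|---|---|
| Event | 6-10% | 3.0 |
| Censored | 12.5% | 4.0 |
| Carried through | 12.5-26% | 4.0-4.7 |

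The event median is 3.0 because the curve drops at month 3 from 0.595 to at most 0.8 × 0.595 = 0.476.

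**4. Confirmation window.** With 28-day cycles the first evaluation, Cycle 2 Day 21, is study day 28 + 21 = 49. Confirmation falls on day 49 + 28 = 77. The next scheduled evaluation, Cycle 4 Day 21, is day 84 + 21 = 105. A first-evaluation responder who leaves between days 49 and 77 can lack confirmation, unless the end-of-treatment scan falls at least 4 weeks after the first response.

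**5. Size for ORR.** One reclassified responder moves the rate by 1/9 = 11 points among the 9 patients at the MTD (10.2), 1/20 = 5 points among the 20 enrolled by the end of escalation (3.4.1), and 1/30 = 3.3 points at the 30-patient maximum. With an assumed 5 responders of 9, ORR is 56% (95% Agresti-Coull 27-81%). Dropping one gives 4/9 = 44% (19-73%).

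**The case against.** **These are descriptive secondary endpoints of a phase 1 trial.** No test rests on them, and MTD and OS definitions are untouched. This stands and limits the weight of the point.

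**EFS and PFS together already bracket the effect.** This stands in part. It works only if SCT is coded as an EFS event, which the plan does not say. The gap between the curves also contains every other new therapy, and the PFS side may rest on time without scheduled assessments.

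**Post-transplant time is not pure credit to the regimen.** This stands. Deaths after SCT are PFS events and, under 6.3.3, end DOR. A post-SCT hazard above the earlier one, not modelled here, would pull the carried-through curve below 12.5%. A reader might also infer that DOR always credits transplant. The documents do not support this: only 10.4.3 clearly does so.

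**Response may not be lost.** A reader might infer that confirmation erases the responses of transplant patients. Nothing shows that patients leave within 4 weeks. A patient transplanted 2 months after response has passed the confirmation date. Footnote 4 puts a scan before new therapy, and outside CTCL the 4-week interval rests on a footnote worded as a recommendation. What remains is that no rule classifies a responder who leaves earlier.

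**The 11 points use the smallest denominator.** This stands. Section 10.4.3 wants every response report to include all patients, where one patient is worth about 3-5 points.

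**Conclusion.** The gap is real: SCT is an intended outcome, and EFS, PFS, DOR and best response lack a coherent rule for it. The same patients can give a 12-month estimate anywhere from 6% to 26% according to the coding alone. That range rests on assumed SCT share, timing and post-SCT hazard, none of which the documents give for this regimen. Medians move less: 3.0 months with SCT as an event, against 4.0-4.7 carried through.

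Two stronger conclusions should not be drawn. One is that EFS definitely scores transplant as failure: the term is undefined, so it only can. The other is that the secondary endpoints cannot describe the regimen: they can, once the coding is stated and both versions are shown. Medians obtained by treating SCT as a DOR event among responders are not evidence about EFS, which starts at enrollment in all patients; no section makes SCT a DOR event.

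**What to change.** 1. **10.4.3:** report PFS, DOR and EFS as defined and, beside them, censored at the last disease assessment on or before the start of SCT conditioning, with the number transplanted.
2. **6.3.4:** state whether SCT in CR or PR is alternative anti-lymphoma therapy, and show EFS both ways.
3. **6.3.1.2, 6.3.3 and 10.4.3:** reconcile these to one DOR censoring date. Censor PFS, DOR and EFS at the last disease assessment instead of last follow-up, unless disease status is collected after SCT.
4. **6.3.2 and calendar footnote 3:** for RECIL patients who leave in response for SCT before the 4-week scan, report ORR with the first documented response counted, and also confirmed-only. State that no scan after conditioning may confirm a response.

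**Cost:** protocol and SAP wording and a second set of curves, with no change to sample size or treatment. Collecting disease status after SCT, if chosen, adds data collection. Censoring at SCT is informative, because transplanted patients are selected for being in response and fit, so these curves supplement the main ones and do not replace them.

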6.3.5 Progression-Free Survival

Progression-free survival (PFS) is defined as the duration of time from the date of study enrollment until time of disease relapse, disease progression, or death, whichever occurs first.

6.3.6 Overall Survival

Overall survival (OS) is defined as the time from the date of study enrollment until time of death from any cause.

6.4 TOXICITY CRITERIA

The following adverse event management guidelines are intended to ensure the safety of each patient while on the study. The descriptions and grading scales found in the revised NCI Common Terminology Criteria for Adverse Events (CTCAE) version 5.0 will be utilized for AE reporting. All appropriate treatment areas should have access to a copy of the CTCAE version 5.0. A copy of the CTCAE version 5.0 can be downloaded from the CTEP web site (http://ctep.cancer.gov/protocolDevelopment/electronic_applications/ctc.htm).

7 NIH REPORTING REQUIREMENTS/ DATA SAFETY MONITORING PLAN

7.1 DEFINITIONS

Please refer to definitions provided in Policy 801: Reporting Research Events found at: <https://irbo.nih.gov/hrpp-policy-guidelines/>.

7.2 OHSRP OFFICE OF COMPLIANCE AND TRAINING / IRB REPORTING

7.2.1 Expedited Reporting

Please refer to the reporting requirements in Policy 801: Reporting Research Events and Policy 802 Non-Compliance Human Subjects Research found at:

<https://irbo.nih.gov/hrpp-policy-guidelines/>.

Note: Only IND Safety Reports that meet the definition of an unanticipated problem or present new information that might affect the willingness of participants to enroll or remain on the study will need to be reported per these policies.

7.2.2 IRB Requirements for PI Reporting at Continuing Review

Please refer to the reporting requirements in Policy 801: Reporting Research Events found at: <https://irbo.nih.gov/hrpp-policy-guidelines/>.

7.3 NCI CLINICAL DIRECTOR REPORTING

Problems expeditiously reviewed by the OHSRP in the NIH eIRB system will also be reported to the NCI Clinical Director/designee; therefore, a separate submission for these reports is not necessary.

In addition to those reports, all deaths that occur within 30 days after receiving a research intervention should be reported via email unless they are due to progressive disease.

To report these deaths, please send an email describing the circumstances of the death to [contact] within one business day of learning of the death.

7.4 NIH REQUIRED DATA AND SAFETY MONITORING PLAN

7.4.1 Principal Investigator/Research Team

The clinical research team will meet at least once weekly when patients are being actively treated on the trial to discuss each patient. Decisions about dose level enrollment and dose escalation will be made during the meeting based on the toxicity data from prior patients and documented in the meeting minutes.

All data will be collected in a timely manner and reviewed by the principal investigator or a lead associate investigator. Events meeting requirements for expedited reporting as described in Section [7.2.1](#) will be submitted within the appropriate timelines.

The principal investigator will review adverse event and response data on each patient to ensure safety and data accuracy. The principal investigator will personally conduct or supervise the investigation and provide appropriate delegation of responsibilities to other members of the research staff.

7.4.2 Safety Monitoring Committee (SMC)

NOTE: CCR SMC was added in an amendment; protocol version 11/12/2021.

This protocol will be periodically reviewed by an intramural Safety Monitoring Committee, comprising physicians, biostatisticians and a lay member selected based on experience, area of expertise, reputation for objectivity, absence of conflicts of interest and knowledge of or experience with clinical trial research. Initial review will occur as soon as possible after the annual NIH Intramural IRB continuing review date. Subsequently, each protocol will be reviewed as close to annually as the quarterly meeting schedule permits or more frequently as may be required by the SMC based on the risks presented in the study. For initial and subsequent reviews, protocols will not be reviewed if there is no accrual within the review period.

The SMC will operate under the rules of an approved charter that will be written and reviewed at the organization meeting of the SMC. Each review will focus on unexpected protocol-specific safety issues that are identified during the conduct of the clinical trial.

Written outcome letters will be generated in response to the monitoring activities and submitted to the Principal investigator and Clinical Director or Deputy Clinical Director, CCR, NCI.

8 SPONSOR PROTOCOL/ SAFETY REPORTING

8.1 DEFINITIONS

8.1.1 Adverse Event

Any untoward medical occurrence in a patient or clinical investigation subject administered a pharmaceutical product and which does not necessarily have a causal relationship with this treatment. An adverse event (AE) can therefore be any unfavorable and unintended sign (including an abnormal laboratory finding), symptom, or disease temporally associated with the use of a medicinal (investigational) product, whether or not related to the medicinal (investigational) product (ICH E6 (R2)).

8.1.2 Serious Adverse Event (SAE)

An adverse event or suspected adverse reaction is considered serious if in the view of the investigator or the sponsor, it results in any of the following:

- Death,
- A life-threatening adverse event (see section [8.1.3](#))
- Inpatient hospitalization or prolongation of existing hospitalization
 - A hospitalization/admission that is pre-planned (i.e., elective or scheduled surgery arranged prior to the start of the study), a planned hospitalization for pre-existing condition, or a procedure required by the protocol, without a serious deterioration in health, is not considered a serious adverse event.
 - A hospitalization/admission that is solely driven by non-medical reasons (e.g., hospitalization for patient or subject convenience) is not considered a serious adverse event.
 - Emergency room visits or stays in observation units that do not result in admission to the hospital would not be considered a serious adverse event. The reason for seeking medical care should be evaluated for meeting one of the other serious criteria.
- Persistent or significant incapacity or substantial disruption of the ability to conduct normal life functions
- A congenital anomaly/birth defect
- Important medical events that may not result in death, be life-threatening, or require hospitalization may be considered a serious adverse drug experience when, based upon appropriate medical judgment, they may jeopardize the patient or subject and may require medical or surgical intervention to prevent one of the outcomes listed in this definition.

8.1.3 Life-threatening

An adverse event or suspected adverse reaction is considered "life-threatening" if, in the view of either the investigator or sponsor, its occurrence places the patient or subject at immediate risk of death. It does not include an adverse event or suspected adverse reaction that, had it occurred in a more severe form, might have caused death. (21CFR312.32).

8.1.4 Severity

The severity of each Adverse Event will be assessed utilizing the CTCAE version 5.0.

